
 ● To evaluate the efficacy of RPT193 administered orally QD for 16 weeks to subjects with moderate-to-severe AD on subject reported symptoms associated with AD. 	
 ● Change from baseline to Week 16 in: 
 ○ Sleep quality (visual analog scale [VAS] from SCORAD) ○ Patient-oriented eczema measure (POEM) ○ DLQI ○ Skin pain NRS ○ Patient global assessment (PtGA) ○ Atopic dermatitis sleep scale (ADSS) ○  ○ Asthma Control Questionnaire (ACQ-5) (in subjects with a history of asthma) ● % of subjects achieving a PtGA score of 0 or 1 and a ≥ 2 point reduction from baseline at Week 2, 4, 8, 12, and 16.

 ● To evaluate the efficacy of RPT193 administered orally QD for 16 weeks to subjects with moderate-to-severe AD in subject subpopulations. 	
 ● % change in EASI in the following subgroups: 
 ○ Prior treatment with dupilumab or tralokinumab (Yes or No) ○ Baseline EASI score of < 21 or ≥ 21 ○ Baseline %BSA of AD affected skin $< 50\%$ or $\geq 50\%$ ○ Baseline vIGA score (3 or 4) ○ Age group ○ Race ○ Ethnicity ○ Pretreatment CCL17 levels ○ Pretreatment CCL22 levels.

Objectives	Endpoints

 Explore durability of treatment effect in those who have demonstrated an objective response at Week 16. 	
 Proportion of subjects maintaining EASI-50 at Weeks 18, 20, 24 among those achieving an EASI-50 at Week 16 and not receiving rescue therapy from Week 8 to Week 16. Proportion of subjects maintaining EASI-75 at Weeks 18, 20, 24 among those achieving an EASI-75 at Week 16 and not receiving rescue therapy from Week 8 to Week 16. Proportion of subjects maintaining EASI-90 at Weeks 18, 20, 24 among those achieving an EASI-90 at Week 16 and not receiving rescue therapy from Week 8 to Week 16. Proportion of subjects maintaining a vIGA score of 0 or 1 at Weeks 18, 20, 24 among those achieving a vIGA score 0 or 1 at Week 16 and not receiving rescue therapy from Week 8 to Week 16.

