
 Explore the durability of the treatment effect after cessation of treatment at Week 16. 	
 % change in EASI at Weeks 18, 20, and 24 compared to Week 16 among those not receiving rescue therapy from Week 8 to Week 16. % change in SCORAD at Weeks 18, 20, and 24 compared to Week 16 among those not receiving rescue therapy from Week 8 to Week 16.
Exploratory (Pharmacokinetic)	

 To evaluate the PK of RPT193 following administration of multiple oral doses of RPT193 administered orally QD for 16 weeks to subjects with moderate-to-severe AD. 	
 PK parameters at Week 2, 4, 8, 12, 16, and 18.
Exploratory (Pharmacodynamic)	

 To evaluate the effect of multiple oral doses of RPT193 administered orally QD for 16 weeks to subjects with moderate-to-severe AD on serum cytokines and chemokines. 	
 Change in serum CCL17 levels Change in serum CCL22 levels Change in serum cytokines.

 To evaluate the effect of multiple oral doses of RPT193 administered orally QD for 16 weeks to subjects with moderate-to-severe AD on peripheral blood T cell subsets. 	
 Change in T cell subset numbers or proportion.

 To evaluate the effect of multiple oral doses of RPT193 administered orally QD for 16 weeks to subjects with moderate-to-severe AD on skin gene expression signatures and microbiome. 	
 Changes in skin gene expression signatures relative to baseline at Week 4, 8, 12, 16, and follow-up using skin tape strips. Change in skin microbiome composition relative to baseline at Week 4, 8, 12, 16, and follow-up.

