6.6.4 Rescue Medications

Subjects who require topical corticosteroids, calcineurin inhibitors, or PDE4 inhibitor medications that could directly impact AD disease activity prior to Day 57 will be withdrawn from study drug and the study if requiring such topical therapies prior to Day 57.

Starting at Day 57, rescue medications for persistent, intolerable AD activity may be considered by the Investigator. Investigators must document evidence of continued active AD with EASI unchanged from or greater than the Baseline EASI score over 2 consecutive visits before initiating therapy. All subjects requiring rescue therapy between Day 57 (Week 8) and Day 113 (Week 16) will remain in the study and on study drug until Week 16.

After the end of treatment at Day 113 and during the follow-up phase, subjects may also initiate rescue if either the subject or investigator feels that there is persistent, intolerable AD activity.

Permitted rescue medications include low- to moderate-potency (class IV-class VII) topical corticosteroids ([Appendix 14](#)) and should be applied only to problem areas. A topical calcineurin inhibitor, topical PDE4 inhibitor (e.g., crisaborole), or low-potency topical steroid may be used on the face if affected. Subjects who require rescue therapy will be considered non-responders for all efficacy endpoints with data imputed for subsequent continuous endpoints for all time points as detailed in the Statistical Analysis Plan (SAP). Ideally, the specified medication for rescue treatment would be supplied by the clinic so that the tube could be weighed prior to administration. In addition, use of the specified medication should be recorded in the e-Diary, and the medication should be brought to clinic at subsequent visits to assess amount of medication used.

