### C. Changes to Planned Analyses from Protocol

The following changes or additions to the planned analyses described in the protocol are noted:

- In Protocol Amendment v2.0, the randomization list is stratified based on region (North America vs. rest of world), baseline vIGA scores (vIGA of 3 vs. 4), and prior dupilumab or tralokinumab use (yes or no). It was later determined that no subjects will be recruited from rest of the world, and therefore stratifying by region in randomization will no longer be required. The existing randomization master list including region as a stratification factor will not be modified or replaced. Any strata related to rest of world region will be disregarded by the IWRS in assigning randomized treatment. All statistical analyses will be adjusted to align with this change by removing region as a stratification factor as applicable.
- Subgroup analysis by pretreatment CCL17/22 levels as required by the protocol is

[REDACTED] ( [REDACTED] ) not included in this SAP. This analysis will be covered by a separate analysis plan for PD data.

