## E. Exploratory Efficacy Analysis

All exploratory efficacy analysis will be based on the FAS. Descriptive summary statistics will be provided by treatment and visit for exploratory endpoints listed below. No imputation will be utilized for missing data.

- Percent change in SCORAD from baseline at Week 2, 4, 8, 12, and 16
- Percent change in BSA from baseline at Week 2, 4, 8, 12, and 16
- Change from baseline to Week 16 in sleep loss from the SCORAD VAS
- Change from baseline to Week 16 in POEM
- Change from baseline to Week 16 in DLQI
- Change from baseline to Week 16 in Skin pain NRS
- Change from baseline to Week 16 in PtGA  
A shift table from baseline will be provided.
- Change from baseline to Week 16 in ADSS  
For item 1 and 3 a shift table will be provided to display the change from baseline. The change from baseline for item 2 will be presented descriptively.

- Change from baseline to Week 16 in ACQ-5  
A shift table from baseline will be provided for each question
- Percent of subjects achieving a PtGA score of 0 or 1 and a  $\geq 2$  point reduction from baseline at Week 2, 4, 8, 12, and 16. The assessment at each specific timepoint will be independently considered.
- Subgroup analysis of the primary efficacy endpoint as outlined in section IV.I
- Proportion of subjects maintaining responder status at Weeks 18, 20, 24 among those achieving the corresponding responder status at Week 16 and not receiving rescue therapy from Week 8 to Week of interest. The endpoint at Week 20 will not consider Week 18 status and will include subjects that do not use rescue from Week 8 to Week 20. Similarly, Week 24 will not consider responder status at Week 18 and Week 20 and will only include subjects that did not use rescue from Week 8 to Week 24. An additional analysis will be conducted without consideration of the use of rescue medication after Week 16. The following responder status will be analyzed separately.
  - EASI-50
  - EASI-70
  - EASI-90
  - vIGA score of 0 or 1
- Percent change in EASI at Weeks 18, 20, and 24 compared to Week 16 among those not receiving rescue therapy from Week 8 to Week of interest. In other words, the analysis at Week 20 will only include subjects who do not use rescue from Week 8 to Week 20.
- Percent change in SCORAD at Weeks 18, 20, and 24 compared to Week 16 among those not receiving rescue therapy from Week 8 to week of interest.

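### SAP VI.E drops subjects rescued during follow-up from the Week 18, 20 and 24 durability analyses; SAP I.C does not list the change, and no analysis scores that rescue as loss of response

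*SAP*

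**What the plan says.** **Protocol.** Table 1 (Section 3.0) sets the population for maintenance of response, using EASI-75 as the example, as subjects "among those achieving an EASI-75 at Week 16 and not receiving rescue therapy from Week 8 to Week 16". EASI-50, EASI-90 and vIGA 0/1 follow the same pattern. The other durability endpoint, percent change, is defined for "EASI at Weeks 18, 20, and 24 compared to Week 16 among those not receiving rescue therapy from Week 8 to Week 16", with a matching endpoint for SCORAD. SAP Section II repeats these definitions.

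**SAP VI.E.** The maintenance analysis is run "among those achieving the corresponding responder status at Week 16 and not receiving rescue therapy from Week 8 to Week of interest". Percent change in EASI is "compared to Week 16 among those not receiving rescue therapy from Week 8 to Week of interest", and the text adds: "In other words, the analysis at Week 20 will only include subjects who do not use rescue from Week 8 to Week 20". The SCORAD item has the same restriction. Within the responder item only, VI.E says: "An additional analysis will be conducted without consideration of the use of rescue medication after Week 16". Its responder list shows EASI-70 where the protocol and SAP Section II have EASI-75.

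**Declared changes.** SAP I.C opens with "The following changes or additions to the planned analyses described in the protocol are noted" and lists two items: dropping region as a stratification factor, and moving the CCL17/CCL22 subgroups to another plan. The durability population is not among them.

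**Scoring of rescue.** Protocol 6.6.4 allows rescue after Day 113 and states: "Subjects who require rescue therapy will be considered non-responders for all efficacy endpoints". SAP IV.D.2 limits treatment-failure imputation to data up to Week 16 and plans no imputation in follow-up.

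**The concern.** Whether responses last after dosing stops is one of the reasons protocol 2.1 gives for the 8-week follow-up. Under 6.6.4, rescue in that period is started because the subject or the investigator judges that the disease remains active and intolerable. Rescue after Week 16 is therefore closely tied to loss of response. Removing rescued subjects from numerator and denominator selects on the outcome being measured.

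Two consequences follow. The reported maintenance percentage can only equal or exceed the figure that scores rescue as failure, provided missing visits are handled alike. And if arms differ in rescue use, the main analysis can show similar maintenance where durability differs.

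The additional analysis does not fill the gap. It restores the protocol population for the responder endpoints, but counts response achieved on rescue medication as maintained response. Follow-up rescue has no EASI threshold, so a rescued subject may still meet EASI-50.

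**Working it through.** The plan gives no figure for follow-up rescue or maintenance, so there is nothing to reproduce. The finding rests on comparing the texts; the arithmetic shows direction and possible size under assumed rates.

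**Which analysis does what at Weeks 18, 20 and 24**

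| | Population: no rescue from Week 8 to | Follow-up rescue scored as |
|---|---|---|
| Protocol Table 1 with 6.6.4, responder endpoints | Week 16 | non-response |
| SAP VI.E main, responder endpoints | week of interest | excluded |
| SAP VI.E additional, responder endpoints | Week 16 | observed status on rescue |
| Protocol Table 1, percent change | Week 16 | 6.6.4 refers to imputation detailed in the SAP |
| SAP VI.E, percent change | week of interest | excluded; no additional analysis |

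**Notation for the responder endpoints.** Of n Week 16 responders without rescue from Week 8 to Week 16, k are rescued by the visit, s of the unrescued miss the visit, a = n - k - s are assessed without rescue, and m of those maintain response. Let r = k/n, d = s/(n - k), p = m/a.

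- Missing visits kept in both denominators: main = m/(n - k); 6.6.4 = m/n; ratio = 1/(1 - r).
- Missing visits dropped from both: main = m/a; 6.6.4 = m/(a + k); ratio = 1 + r/((1 - r)(1 - d)), which is at least 1/(1 - r).

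So 1/(1 - r) is exact or a lower bound. The SAP does not settle the convention: IV.J takes percentages of the analysis population unless stated otherwise, while VI.E says only that missing data are not imputed.

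**Assumed p = 90%, no missing visits.** The additional analysis is (1 - r)p + r·g, where g is the share of rescued subjects who meet the criterion on rescue, assumed 30-60%.

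| r | Main | 6.6.4: (1 - r) × 90% | Ratio | Additional |
|---|---|---|---|---|
| 0% | 90% | 90% | 1.00 | 90% |
| 10% | 90% | 81% | 1.11 | 84-87% |
| 20% | 90% | 72% | 1.25 | 78-84% |
| 30% | 90% | 63% | 1.43 | 72-81% |
| 40% | 90% | 54% | 1.67 | 66-78% |

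**With d = 10%** (the whole-study drop-out assumption in protocol 5.5, borrowed only as an example), for r = 10, 20, 30, 40%:

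- Kept in both: main 0.9 × 0.9 = 81%, against 72.9, 64.8, 56.7, 48.6%. The ratio is still 1/(1 - r).
- Dropped from both: main 90%, against 80.1, 70.4, 61.0, 51.7%. The ratio is 1.12, 1.28, 1.48, 1.74.

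**Between arms**, p = 90% in both, r = 10% versus 40%, no missing visits:

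- Main: 90 - 90 = 0 points.
- 6.6.4: 81 - 54 = 27 points.
- Additional: 84 - 66 = 18 points (g = 30%) to 87 - 78 = 9 points (g = 60%).

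A second example: 60% of Week 16 responders in one arm and 40% in the other maintain response without rescue, with rescue of 10% and 40%. Scoring rescue as failure gives 60 - 40 = 20 points. The main analysis gives 60/90 = 66.7% versus 40/60 = 66.7%, so 0 points.

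**Percent change.** If rescued subjects have mean μr and unrescued subjects μu, adding the rescued moves the mean by (1 - r)μu + r·μr - μu = r·D, with D = μr - μu. An assumed D of 25-50 points gives 2.5-5 points at r = 10%, 5-10 at 20% and 10-20 at 40%. The sign depends on which post-rescue values are used. With μu = +10 and r = 20%, μr = +60 gives a mean of +20, while μr = -20 (improved by rescue) gives +4.

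**Scale.** SAP III.D expects about 60 completers per arm. An assumed 20-40% Week 16 response gives 12-24 responders per arm, so r = 20% is about 2-5 subjects.

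**The case against.** The best counter-argument is that 6.6.4 is one sentence in a section on rescue medication, and that it goes on to defer to the SAP. If it governed these endpoints, a subject rescued between Weeks 8 and 16 would already be a Week 16 non-responder, and the Table 1 exclusion would be redundant. On this view the protocol handles rescue in the durability endpoints by exclusion, and VI.E merely extends that.

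This does not succeed. The deferral to the SAP attaches to imputing continuous data, not to the non-responder rule. The Week 8 to 16 clause is not redundant, because protocol 9.4.5 derives binary response for the key secondary endpoints, up to Week 16, from imputed scores; a rescued subject can therefore be a Week 16 responder. For follow-up, 6.6.4 is the only protocol sentence on how a rescued subject is scored.

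Several points do stand:

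- The additional analysis restores the protocol population for the responder endpoints.
- Up to Week 16, the treatment-failure analyses do count post-rescue data as failure.
- SAP VII.G summarises rescue incidence and time to first rescue, so differing rescue use would not be invisible. Those summaries are not restricted to Week 16 responders by visit.
- EASI-70 is probably a typing error.
- If post-rescue values were set to missing and not imputed, the percent-change mean in the protocol population would equal the VI.E mean. The shift arises only if those values are used or imputed.
- Every rate above is assumed, and VI.E states its rule openly, with worked examples.

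**Conclusion.** The point holds. VI.E contradicts both protocol Table 1 and the SAP's own Section II, and I.C does not declare the change. No Week 18, 20 or 24 analysis scores follow-up rescue as non-response. The percent-change population in the protocol is not analysed. As written, VI.E has no EASI-75 maintenance analysis.

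For the responder endpoints the direction is certain when missing visits are handled alike: the main figure equals or exceeds the 6.6.4 figure, by a factor of at least 1/(1 - r) whenever any response is maintained. The size depends on follow-up rescue among Week 16 responders, which the documents do not give; with no rescue there is no effect. For percent change, both size and sign depend on a handling of post-rescue values that the SAP does not state.

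The endpoints are exploratory and descriptive, so the primary test and its type I error are untouched. This should be corrected because it bears on a question the follow-up period is there to answer, but it does not threaten the trial's main conclusion.

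**What to change.** In SAP VI.E:

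1. Use the protocol population, no rescue from Week 8 to Week 16, for all durability endpoints.
2. For EASI-50, EASI-75, EASI-90 and vIGA 0/1, present an analysis in which rescue started after Week 16 and by the visit counts as not maintaining response. Keep the rescue-free and rescue-ignored versions as supportive.
3. Correct EASI-70 to EASI-75.
4. Show the number of Week 16 responders rescued by visit and arm, and state one rule for missing visits that applies to every version.
5. For percent change in EASI and SCORAD from Week 16, add the protocol-population analysis and state how post-rescue values are handled. Setting them to missing without imputation would only reproduce the current VI.E mean.
6. List any remaining departure from the protocol in I.C.

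The cost is SAP wording and programming, with no new data. Reported maintenance percentages will be equal or lower; percent-change means may move either way.

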## VII. Safety Analyses

All safety analysis will be based on the safety analysis set. The safety analyses which need analysis window, eg. change from baseline, will follow the analysis window for efficacy data, unless it is specified in each section below.

### A. Exposure

Study drug administration data will be listed by subject. The following exposure parameters will be summarized by treatment group and overall using descriptive statistics:

- Total duration of exposure (days), defined as the (date of last dose- date of first

[REDACTED] dose) +1

- The total number of tablets dispensed, defined as the number of bottles dispensed multiplied by 32. There are 32 tablets in a bottle.
- The total number of tablets returned according to drug accountability from EDC, defined as the number of tablets returned. If a bottle is not returned it will be assumed that no tablets were taken from that bottle
- Planned doses, defined as two tablets for duration of the study therefore 224 tablet.
- The total number of tablets taken, is number of dispensed tablets minus total number of tablets returned.
- Treatment compliance, defined as the (total number of tablets taken/ total number of tablets planned)\*100%

Treatment compliance will be summarized as a continuous variable as well as a categorical variable for the categories of <80% and ≥ 80%, <90% and ≥ 90%, <120% and ≥ 120%

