6.1 Study Treatment(s) Administered

RPT193-02 will consist of daily administration of 50, 200, or 400 mg of RPT193 or placebo for 16 weeks (112 consecutive days). The study drugs will be administered orally at approximately the same time of the day. On study days where PK samples are to be collected, the subject will administer the study drug at the study center, following the PK sample collection. The date and time of study drug administration will be collected daily via an electronic Diary (e-Diary) provided to the subject whether study drug is taken on- or off-site. The subject will be instructed to take the study drug at approximately the same time of the day when taken off-site. The subject will complete an e-Diary to document the time of each dose taken when off-site. Also, in the event of an adverse event of the gastrointestinal system organ class, the subject may be asked to indicate the timing of taking product in relation to food intake.

Further details regarding the study treatments can be found in [Table 2](#).

Table 2 Study Treatment Details

	Study Treatments	
Product name	RPT193	Placebo
Dosage form	Tablet	Tablet
Route of administration	Oral	Oral
Source of procurement of active substance	██████████ ██████████	Not applicable
Manufacturer	██████ ██████████	██████ ██████████

The contents of the label will be in accordance with all applicable regulatory requirements. Details on study drug preparation by ████████ can be found in the Manufacturing Batch Record. The active medication will be provided by the Sponsor.

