### 3. Per-protocol Set

All subjects in FAS with no major protocol deviation that would have an impact on the primary and key secondary efficacy assessments will be included in the per-protocol (PP) set. Major protocol deviations will be reviewed and determined prior to database lock and unblinding.

Subjects may be excluded from the PP for the following, but not limited, to violations:

- Did not meet inclusion/exclusion criteria
- Was not compliant with study treatment
- Received incorrect treatment

Subjects to be excluded from the PP analysis set will be determined based on a blinded data review meeting prior to database lock.

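### The compliance formula divides by 224 tablets for every subject and counts an unreturned bottle as untaken, so the compliance table mixes early stopping with poor adherence

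*SAP*

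**What the plan says.** SAP VII.A builds compliance from four rules:

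- Denominator: "Planned doses, defined as two tablets for duration of the study therefore 224 tablet". Nothing adjusts it for a subject who stops early.
- Numerator: "The total number of tablets taken, is number of dispensed tablets minus total number of tablets returned". On bottle size: "There are 32 tablets in a bottle".
- Missing bottles: "If a bottle is not returned it will be assumed that no tablets were taken from that bottle".
- Ratio: "total number of tablets taken/ total number of tablets planned", times 100%, summarised as a continuous variable and split at 80%, 90% and 120%.

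The same list defines each subject's duration of exposure as last dose date minus first dose date plus one, but compliance does not use it. The SAP defines no other compliance measure.

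SAP IV.H.3 names "Was not compliant with study treatment" among the reasons for which a subject may be left out of the per-protocol set. It gives no cut-off, does not refer to VII.A, and leaves the decision to a blinded review before database lock. The only numeric definition is in Protocol 6.4, where significant non-compliance means more than 20% of doses missed. Protocol 6.1 and 6.4 also have the date and time of each dose entered daily in an e-Diary, on site and at home.

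**The concern.** Adherence asks whether a subject took the tablets due while on treatment. Persistence asks how long the subject stayed on treatment. A constant denominator of 224 merges the two, so a subject who followed instructions exactly and then stopped looks like one who skipped doses.

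Some of these stops are required by the Protocol: withdrawal if certain topical therapies are needed before Day 57 (6.6.4), discontinuation of dosing for specified adverse events (7.2.1), and withdrawal for the laboratory abnormalities in Table 4 (7.2.2). Such stops may depend on efficacy or safety, so the distortion could differ between arms.

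The missing-bottle rule adds a second error. Protocol 6.2 foresees that drug will sometimes not be returned. Assuming that nothing was taken is one extreme of what may have happened, and it lowers the count of tablets taken as well as the percentage.

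At stake are the by-arm compliance and exposure tables and, less directly, membership of the per-protocol set. That set is used for sensitivity analyses of the primary endpoint (SAP VI.B and VI.C) and the key secondary endpoints (SAP VI.D.1).

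**Working it through.** **Inputs.** Two tablets a day, 224 planned tablets and 32 tablets per bottle (SAP VII.A); a 112-day course (Protocol 6.1); an 80% split (SAP VII.A), which matches more than 20% of doses missed (Protocol 6.4).

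**1. The plan's own figure.** 2 × 112 = 224. It reproduces exactly.

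**2. Early stop, every tablet taken, all bottles returned.** Score = 2 × (day of last dose) / 224. No dispensing assumption is needed.

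| Last dose | Tablets taken | Score under VII.A | Taken / (2 × days on treatment) |
|---|---|---|---|
| Day 28 | 56 | 25.0% | 100% |
| Day 56 | 112 | 50.0% | 100% |
| Day 84 | 168 | 75.0% | 100% |
| Day 89 | 178 | 79.5% | 100% |
| Day 90 | 180 | 80.4% | 100% |
| Day 100 | 200 | 89.3% | 100% |
| Day 112 | 224 | 100% | 100% |

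Day 89 is the latest last dose that scores below 80%, and Day 100 the latest below 90%. A subject withdrawn for topical therapy before Day 57 cannot exceed 112/224 = 50%.

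**3. Unreturned bottles, full course, every tablet taken.** Score = (224 − tablets used from the missing bottles) / 224.

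- One bottle, all 32 used: 192/224 = 85.7%, a loss of 32/224 = 14.3 points. This is the worst case.
- One bottle, 24 used: 200/224 = 89.3%. With 24 or more used, the subject falls below 90%.
- Two bottles, all 64 used: 160/224 = 71.4%, again the worst case.
- Two bottles, 24 used from each: 176/224 = 78.6%.

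The 24-tablet figure rests on an assumption, since the documents do not give bottles per visit. It takes the fewest bottles that cover dispensing on Days 1, 15, 29, 57 and 85, which is 1 + 1 + 2 + 2 + 2 = 8. In a 28-day interval needing 56 tablets, one bottle is then emptied (32) and 24 are taken from the other. The 14.3-point maximum per bottle does not depend on this.

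**4. One missing bottle plus some missed doses.** Suppose the bottle would have supplied 28 of the 224 tablets (a 14-day interval). The score is true adherence × (224 − 28)/224 = true adherence × 0.875. True adherence of 90% scores 78.8%, and anything below 0.80/0.875 = 91.4% scores below 80%.

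**The case against.** The strongest case on the other side is that the fixed denominator is a choice of definition. It measures the share of the planned course taken, and a subject who stopped on Day 56 did receive half of it. Duration of exposure is reported in the same section, and discontinuations with reasons appear under disposition (SAP V.A), so early stopping can be seen elsewhere. This stands as a reason to keep the share of 224 as an exposure measure. It does not justify labelling that share treatment compliance and splitting it at the level the Protocol uses for missed doses.

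A reader might also infer more than the documents support:

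- **That the VII.A score decides per-protocol exclusion.** SAP IV.H.3 does not cite VII.A and sets no threshold. Protocol 6.4 assesses adherence by questioning as well as drug records, and the blinded reviewers could also see exposure duration and discontinuation reasons. The link is plausible but inferred.
- **That the primary result is biased.** The primary and key secondary analyses use the full analysis set. The per-protocol analysis is one of seven sensitivity analyses listed for the primary endpoint.
- **That one lost bottle makes an adherent completer non-compliant at 80%.** It leaves at least 85.7%. Crossing 80% takes two bottles, a last dose by Day 89, or one bottle with some missed doses.
- **That tablets in unreturned bottles were usually taken.** The documents give no evidence either way and no frequency of non-return.
- **That the error always runs downward or differs by arm.** Tablets lost from a returned bottle count as taken, which pushes upward. A difference between arms is possible, but the Protocol gives only one overall dropout assumption of 10%.
- **That the e-Diary is a complete record.** Protocol 6.4 provides for subjects missing more than 20% of entries.

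**Conclusion.** The point holds for the compliance and exposure summaries. As defined, compliance does not measure adherence for anyone who stops early, and tablets taken are understated wherever tablets were used from a bottle that did not come back. The early-stop result (below 80% for any last dose on or before Day 89, 50% at Day 56) follows from the SAP's own figures. The bottle results are bounds: 85.7% or higher with one missing bottle, as low as 71.4% with two.

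How many subjects are affected is unknown. Ten per cent of the SAP's planned 268 is about 27 dropouts, but the documents do not say how many would stop by Day 89.

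An effect on the per-protocol sensitivity analyses is possible but not established. It would arise only if the reviewers used this score with an 80% cut-off. Blinding would not remove it, because they would be reading the same score. The full analysis set results do not depend on it.

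**What to change.** Amend SAP VII.A and IV.H.3 as follows.

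1. **Denominator.** Planned tablets = 2 × (date of last dose − date of first dose + 1 − days of documented investigator-directed interruption). Without the subtraction, a hold allowed under Protocol 7.1.1 would count as missed doses: 14 days is 28 tablets, or 28/224 = 12.5 points over a full course.
2. **Exposure.** Report the share of the full 224-tablet course separately, under that name.
3. **Unreturned bottles.** Take tablets used from the e-Diary dosing record for that dispensing interval. Where the diary is also missing, remove the interval from both numerator and denominator. For an adherent completer lacking one 28-day interval, this gives (224 − 56)/(224 − 56) = 100%. Setting only the bottle's count to missing and keeping the denominator would reproduce the present result.
4. **Per-protocol review.** State that the blinded review uses this adherence measure and considers early discontinuation separately. The second part is needed because a subject who stops on Day 10 having taken every tablet due would score 100%.

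The cost is SAP wording and minor programming on data already collected, with some intervals left without usable compliance data. SAP I.B allows changes until unblinding, and SAP IV.F has a limited sponsor team receiving unblinded Week 16 results before database lock. The change should therefore be settled before that analysis and before the blinded review.
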